#### **5.2.3 Safety Analysis Set**

The SafAS is defined as those subjects who have received at least one dose of the study vaccines. All subjects will have their safety analyzed after each dose according to the vaccine they actually received, and after any dose according to the vaccine received at first dose.

The safety data will also be presented separately for dengue immune, non-immune / undetermined subjects.

Safety data recorded for a vaccine received out of the protocol design will be excluded from the analysis (and listed separately).

Note: Subject will be included in the “any dose” analysis according to the 1st dose received that corresponds to a protocol group.

#### **5.2.4 Other Analysis Set**

##### ***Randomized subjects***

A randomized subject is a subject for whom an injection group has been allocated.

### **5.2.5 Populations Used in Analyses**

The main immunogenicity analyses (non-inferiority tests) will be performed on the per protocol analyses sets PPG and PPC respectively for Gardasil and CYD dengue vaccine comparisons and will be confirmed on the FAS immune subject. The subjects will be analyzed by the vaccine group to which they were randomized.

All other immunogenicity analyses will be performed on the FAS and by baseline dengue status. Subjects will be analyzed by the vaccine group to which they were randomized.

The safety analyses will be performed on the SafAS. Subjects will be analyzed according to the vaccine they actually received and by baseline dengue status.

## **5.3 Handling of Missing Data and Outliers**

### **5.3.1 Safety**

No replacement will be done.

In all subject listings, partial and missing data will be clearly indicated as missing.

#### **5.3.1.1 Immediate**

For unsolicited non-serious systemic AEs, a missing response to the “Immediate” field will be assumed to have occurred after the 30-minute surveillance period and will not be imputed.

For SAEs, missing or partially missing elapsed time from last vaccination recorded will remain missing and not be imputed. Such SAEs will not be considered as immediate.

#### **5.3.1.2 Causality**

Missing causality (relationship) for unsolicited non-serious AEs and SAEs will be considered at the time of analysis as related to vaccination.

#### **5.3.1.3 Measurements**

Partially missing temperatures will be handled as described in Section 4.4.1.1.1.

#### **5.3.1.4 Intensity**

For solicited reactions, missing intensities will be handled as described in Section 4.4.1.1.1.

For unsolicited non-serious AEs, missing intensities will remain missing and will not be imputed.

### 5.3.1.5 Start Date and Stop Date

Missing or partially missing start dates for unsolicited AEs will remain missing and not be imputed. If either the start or stop date is missing or partially missing, the time of onset will be considered to be missing. Nevertheless unsolicited AEs with missing time of onset will be included in analyses according to the visit collected.

Missing or partially missing stop dates for AEs (solicited reactions and unsolicited AEs) will remain missing and not be imputed.

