An unsolicited AE is an observed AE that does not fulfill the conditions prelisted in the CRF in terms of diagnosis and/or onset post-vaccination, i.e., excluding solicited reactions, e.g., if headache between D0 and D14 is a solicited reaction (i.e., prelisted in the CRF), then a headache starting on D14 is a solicited reaction, whereas headache starting on D15 post-vaccination is an unsolicited AE.

An unsolicited non-serious AE is an unsolicited AE excluding SAEs.

Injection Site Reaction:

An injection site reaction^a is an AR at and around the injection site. Injection site reactions are commonly inflammatory reactions.

Systemic AE:

Systemic AEs are all AEs that are not injection site reactions. They therefore include systemic manifestations such as headache, fever, as well as localized or topical manifestations that are not associated with the vaccination site, e.g., erythema that is localized but that is not at the injection site.

Adverse Events of Special Interest (AESIs):

AEs of special interest are AEs that are considered by the Sponsor to be relevant for the monitoring of the safety profile of the investigational vaccine.

^a All injection site AEs are considered to be related to vaccination and are therefore all *injection site reactions*.

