##### 4.4.1.2.3 Time of Onset

Time of onset in days following the vaccination will be computed as follows:

- Time of onset = start date – date of previous vaccination

If the start date of the AE is the same as the last vaccination date, then the onset is “0”.

If one of the dates is partially missing, time of onset will be considered as “Missing”. Events that occur before vaccination (negative time of onset) will not be included in the analyses but will be listed separately. The unsolicited non-serious AEs will be analyzed within 28 days after vaccination, which corresponds to AEs with a time of onset between 0 and 28 days after vaccination or missing. An AE with missing time of onset will be considered to have occurred just after the vaccination indicated by the visit number, so will be included in these tables.

Time of onset will be displayed by period as follows:

- D0-D3
- D4-D7
- D8-D14
- $\geq$  D15
- Missing

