#### 4.4.1.2.4 Duration

The duration will be computed as: Duration = stop date of event - start date of event + 1.

If start or stop dates are unfilled (“blank”) or missing (contain “MD”) or ongoing is ticked, then the duration will be considered as “Missing.”

If the start date of the AE is the same as the last vaccination date, then the duration is 1 day.

Duration will be displayed by period as following:

- 1-3 days
- 4-7 days
- 8-14 days
- 15 days or more
- Missing

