##### 4.4.1.3.2 Time of Onset

Time of onset will be computed using the same methodology as for unsolicited non-serious AEs described in Section 4.4.1.2.3.

SAEs will be analyzed throughout the study using the following periods:

- Within 28 days after each/any injection
- During the study (i.e., all SAEs occurred during the study)

An SAE with missing time of onset will be considered to have occurred after the vaccination indicated by the visit number, so will be included in these tables.

Note: SAEs that occurred before vaccination (negative time of onset) will not be included in analysis, but will be listed separately.

Note for SAEs: Elapsed time from last vaccination recorded will be calculated if the SAE occurred within 24 hours of vaccination.

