##### ***Safety***

All analyses will be descriptive; no hypotheses will be tested. Safety will be assessed for all subjects and for immune subjects after each and any dose of Gardasil and CYD Dengue vaccine. Moreover, a complementary analysis will be performed for each dose of CYD dengue vaccine, for each and any group, on non-immune subjects.

As there are differences in the intensity considered for measurable reactions depending on ages of subjects, a complementary analysis will be performed according to the following age groups: 9-11 years and 12 to 13 years.

For the main parameters, 95% CIs of point estimates will be calculated using the normal approximation for quantitative data and the exact binomial distribution (Clopper-Pearson method, quoted by Newcombe) for single proportions.

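### SAP 5.3.1.5 sets a known time of onset to missing when only the stop date is incomplete, which conflicts with 4.4.1.2.3 and can put late SAEs in the 28-day table

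*SAP*

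**What the plan says.** Two parts of the SAP define time of onset for unsolicited events.

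- **Section 4.4.1.2.3 (derivation).** The formula is "Time of onset = start date – date of previous vaccination". The rule for incomplete dates follows it: "If one of the dates is partially missing, time of onset will be considered as" missing. The only dates in the formula are the event's start date and the vaccination date.
- **Section 5.3.1.5 (missing data).** "If either the start or stop date is missing or partially missing, the time of onset will be considered to be missing". Events whose onset becomes missing are still analysed, according to the visit at which they were collected.

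For SAEs, section 4.4.1.3.2 says "Time of onset will be computed using the same methodology as for unsolicited non-serious AEs" and points to 4.4.1.2.3. It lists two analysis periods: the 28 days after each or any injection, and the whole study. It then adds "An SAE with missing time of onset will be considered to have occurred after the vaccination indicated by the visit number", and such events go into the tables just listed.

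The stop date enters through section 4.4.1.2.4, which computes duration. If the start or stop date is blank or missing "or ongoing is ticked, then the duration will be considered as" missing.

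**The concern.** The SAP contains two written derivations of one variable and does not say which prevails. The version in 5.3.1.5 discards information that is in hand: when the start date is complete, the onset is known whatever happened to the stop date.

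For SAEs this goes beyond a label. Missing onset is treated inclusively, which is reasonable when the start date is truly unknown. Combined with 5.3.1.5, the same inclusive rule would move an event known to have begun months after an injection into the 28-day post-injection table. That table is where a reader looks for events close in time to vaccination. In a table with few SAEs, one such event would be visible.

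For non-serious events the stakes are lower. They are collected only for Days 0–28, so the main effect is that a known onset day is shown in the missing category.

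**Working it through.** No sample-size or power figure is involved. The check is to run both rules on the same records.

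**Inputs**

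- Rule A (SAP 4.4.1.2.3): onset = start date − vaccination date; missing only if one of those two dates is incomplete.
- Rule B (SAP 5.3.1.5): as Rule A, but also missing if the stop date is missing or partial.
- Inclusion in the 28-day table (SAP 4.4.1.2.3 and 4.4.1.3.2): onset from 0 to 28, or onset missing.

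**Results, with vaccination on day 0**

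| Record | Rule A onset | In 28-day table? | Rule B onset | In 28-day table? |
|---|---|---|---|---|
| Start day 10, stop day 12 | 10 | yes | 10 | yes |
| Start day 10, stop missing | 10 | yes | missing | yes |
| Start day 28, stop missing | 28 | yes | missing | yes |
| Start day 29, stop missing | 29 | no | missing | **yes** |
| Start day 60, stop day 65 | 60 | no | 60 | no |
| Start day 60, stop missing | 60 | no | missing | **yes** |
| Start day 150, stop missing | 150 | no | missing | **yes** |
| Start missing, stop day 65 | missing | yes | missing | yes |

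The rules disagree on table membership for one class of record only: a known start after day 28 with an incomplete stop date. A start on day 120 gives 120 − 0 = 120 under Rule A (out) and missing under Rule B (in).

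**Does 5.3.1.5 reach SAEs?** It refers to unsolicited AEs without the non-serious qualifier. Protocol 9.2.2.1 says "An unsolicited non-serious AE is an unsolicited AE excluding SAEs", so the unqualified term can be read to include SAEs.

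**Can such records arise?** SAEs are collected until 6 months after the last vaccination (Protocol 9.2.2.3.4). On the nominal schedule, with a month taken as 30.4375 days, the time beyond day 28 after the latest injection is:

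- Group 1: injections at months 0, 6 and 12; follow-up 18 × 30.4375 ≈ 548 days. Days within windows: 3 × 29 = 87. Outside: 548 − 87 = 461, and 461/548 = 84%.
- Group 2: injections at day 0, day 28, month 6, month 6 + 28 days and month 12 + 28 days; follow-up 28 + 548 = 576 days. Days within windows: 28 + 29 + 28 + 29 + 29 = 143. Outside: 576 − 143 = 433, and 433/576 = 75%.

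Most SAE follow-up time therefore lies where a misplacement is possible. This describes opportunity; it does not predict a count.

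**Size per misplaced event**, in a subject with no other SAE in the window:

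- All-subjects table, planned group size: 1/264 = 0.0038, or 0.38 percentage points.
- Dengue-immune table, assuming 121 immune subjects per group (the threshold for testing the co-primary objectives): 1/121 = 0.0083, or 0.83 percentage points.
- Whole-study SAE table: 0.

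**The case against.** The conflict between the two sections is hard to dispute. The case against is about the SAE consequence, and it has four parts.

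1. **The SAE section has its own route.** It points to 4.4.1.2.3, not 5.3.1.5, and other parts of 5.3.1 name SAEs when they are meant. A programmer following 4.4.1.3.2 would get onset 120. This is a fair reading, but 5.3.1.5 does not use the non-serious qualifier that its neighbouring sections use, and the protocol's definition supports the wider scope. On the narrow reading the contradiction still stands for non-serious events.
2. **The inclusion wording is softer for SAEs.** Section 4.4.1.2.3 places non-serious events with missing onset just after the vaccination and expressly admits them to the 28-day analysis. Section 4.4.1.3.2 says only that they occurred after it. However, the tables it then refers to include the 28-day one, and nothing excludes these SAEs from it.
3. **Ongoing is not the same as missing.** Section 4.4.1.2.4 treats ongoing as a separate state, and a footnote in Protocol 9.2.2.3.3 regards AEs with no stop date obtained as ongoing at the end of the trial. If that footnote extends to SAEs, the affected records shrink largely to those with partial stop dates.
4. **SAE records are well maintained.** Prompt updating (Protocol 10.2), reconciliation before database release (11.2) and follow-up of related unresolved events (5.1.4) all make incomplete stop dates less likely.

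Parts 3 and 4 narrow how often the problem would occur. None of the four removes the contradiction. It is also right that 0.83 points is not an upper limit: 121 is a per-protocol testing threshold, and the immune safety subset could be smaller or larger.

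**Conclusion.** The concern holds. Section 5.3.1.5 is wrong as written: it makes onset depend on a date that plays no part in the onset formula, and it discards a known value. The contradiction with 4.4.1.2.3 is plain on the text. The 28-day SAE consequence follows if 5.3.1.5 is applied to SAEs as worded and missing-onset SAEs enter both of the listed tables. Both are the more natural readings, but neither is the only one.

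The practical weight is limited. On safety the SAP says "All analyses will be descriptive; no hypotheses will be tested", so no test, primary endpoint or power figure is touched. The documents do not give the number of SAEs with an incomplete stop date, and it may be zero. The per-event sizes of 0.38 and 0.83 percentage points are illustrations from assumed denominators. The correction should be made because it is nearly free and the alternative leaves the choice of rule to the programmer.

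**What to change.** In the onset sentence of SAP 5.3.1.5, delete *either* and *or stop*, so that onset is missing only when the start date is missing or partial. The vaccination date may be named there too for completeness, although 4.4.1.2.3 already covers it. An incomplete stop date then affects only duration, as 4.4.1.2.4 provides. Events with a truly unknown start are still included by visit, so that rule stays unchanged.

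After the change, SAEs starting on day 29, 60 or 150 with no stop date keep those onsets and stay out of the 28-day table. Those starting on day 10 or 28 stay in.

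The cost is a few words in one sentence and a check of the derivation program against 4.4.1.2.3. It needs no new rule and no data collection.

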9.2.2.3.3 Unsolicited Non-serious Adverse Events From Day 0 to Day 28After Each Vaccination

In addition to recording solicited reactions, subjects or legally acceptable representatives will be instructed to record any other medical events that may occur during the 28-day period after each vaccination to be taken as per the trial design. Space will be provided in the DC for this purpose.

For each unsolicited non-serious AE, the following information is to be recorded:

- Start and stop dates^a
- Intensity of the event:
 - For measurable unsolicited non-serious AEs that are part of the list of solicited reactions, the size of the AE as well as the temperature for fever will be collected and analyzed based on the corresponding scale used for solicited reactions (see Table 9.1 to Table 9.3)
 - Other unsolicited non-serious AEs will be classified according to the following intensity scale:
 - Grade 1: No interference with activity
 - Grade 2: Some interference with activity
 - Grade 3: Significant; prevents daily activity
- Action taken for each AE, if any (e.g., medication)

The action taken by the subject or legally acceptable representative to treat any **unsolicited AEs** will be classified in the CRF using the following scale:

- 0: None
- 1: Medication (self-medication with an existing prescription or over-the-counter medication)
- 2: Health care provider contact (no new medication prescribed)

^a The stop date of all related AEs will be actively solicited. For other events, the investigator will provide the stop date when it becomes available. AEs for which no stop date was obtained during the course of the trial will be considered as ongoing at the end of the trial.

- 3: Health care provider contact and prescription of a new medication (health care provider instructed subject to take a new medication, either an over-the-counter medication or one requiring a written prescription)
- Whether the AE led to discontinuation
- Whether the AE was related to vaccination (for unsolicited systemic AEs)

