#### 4.4.1.1.6 Overall Number of Days of Occurrence

If a reaction is ongoing at the end of the solicited period, then the overall number of days of occurrence is derived from the daily intensities and the stop date of the reaction after the end of the solicited period. The overall number of days of occurrence is:

- $(\text{stop date} - \text{last vaccination date}) + (\text{number of days of occurrence within the solicited period}) - \text{length of the solicited period} + 1$

If the stop date is missing or incomplete (contains missing data [MD]), the overall number of days of occurrence will be considered as "Missing".

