#### **4.4.1.3.3 Duration**

Duration will be computed using the same methodology as for unsolicited non-serious AEs described in Section 4.4.1.2.4 .

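### Ongoing and partly dated adverse events are tabulated with duration 'Missing' even when the recorded data already place them in the longest duration category

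*SAP*

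**What the plan says.** For unsolicited non-serious AEs, SAP 4.4.1.2.4 defines "Duration = stop date of event - start date of event + 1". It makes the duration missing when a start or stop date is blank or incomplete, "or ongoing is ticked, then the duration will be considered as" 'Missing'. The highest display category is "15 days or more", followed by a separate 'Missing' row. SAP 4.4.1.3.3 carries this over to SAEs: "Duration will be computed using the same methodology as for unsolicited non-serious AEs described in Section 4.4.1.2.4".

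For solicited reactions that continue past the solicited period, SAP 4.4.1.1.6 has the same rule: "If the stop date is missing or incomplete (contains missing data [MD]), the overall number of days of occurrence will be considered as" 'Missing'. The top rows of Table 4.6 are ≥ 8 days (injection site) and ≥ 15 days (systemic), again with a 'Missing' row.

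SAP 5.3.1.5 sets the general principle for stop dates: "Missing or partially missing stop dates for AEs (solicited reactions and unsolicited AEs) will remain missing and not be imputed".

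Protocol 9.2.2.3.3, footnote a, adds a default status: "AEs for which no stop date was obtained during the course of the trial will be considered as ongoing" when the trial ends. The same footnote says that stop dates are actively sought for related AEs. For other events the investigator supplies the date if it becomes available.

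Neither document uses a known minimum duration to assign a category, and no duration table has an 'Ongoing' row.

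**The concern.** An event that was observed to be still present, or that stopped in a known later month, has a duration with a known lower bound. If that bound already reaches the open-ended top category, the category is known although the exact duration is not. The SAP rule discards this knowledge.

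The loss has a direction. Among events whose category can be recovered in this way, all belong in the top row and none is shown there. Protocol 9.2.2.2 lists duration among the possible descriptors of the safety endpoints, so a reader of the duration tables could take persistent events for incomplete data.

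The rule also runs against the SAP's handling of other incomplete safety data, which is conservative. Missing causality counts as related (5.3.1.2), and a reaction too large to measure counts as Grade 3 (4.4.1.1.1).

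**Working it through.** No sample size, power or error rate depends on this rule, so there is no stated figure to reproduce. The check applies the SAP's own formula to worked cases and compares the SAP's result with the documented minimum. A minimum can settle only an open-ended top row.

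**1. Partial stop date (unsolicited AE or SAE).** Minimum = earliest possible stop date − start date + 1.
- Illustrative case: start 5 March, stop in May with the day missing.
- Earliest stop 1 May: 57 + 1 = 58 days. Latest stop 31 May: 87 + 1 = 88 days.
- Every possible value is at least 15 days. The SAP result is 'Missing'.

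**2. Solicited reaction that is ongoing under SAP 4.4.1.1.7.** That section requires a grade on the last solicited day and a grade in the ongoing period. Minimum = days counted in the solicited period + 1.
- Injection site, graded on all of D0–D7: 8 + 1 = 9 days, so ≥ 8 is certain.
- Systemic, graded on all of D0–D14: 15 + 1 = 16 days, so ≥ 15 is certain.
- Injection site, onset only on D7: 1 + 1 = 2 days, so the category is not settled.
- With an incomplete stop date, the SAP result is 'Missing' in all three cases.

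**3. Unsolicited non-serious AE documented as present at V08.** V08 is 28 (+14) days after the third CYD injection. Minimum = day of V08 − onset day + 1.
- V08 at D28: onset D14 gives 28 − 14 + 1 = 15 days, settled. Onset D20 gives 28 − 20 + 1 = 9 days, not settled.
- V08 at D42: onset D28 gives 42 − 28 + 1 = 15 days, so any onset in the D0–D28 analysis window is settled.

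**4. SAE, or related AE followed to resolution, documented as present at the 6-month contact.** Taking that contact as about D182 (an assumption), onset D28 gives 182 − 28 + 1 = 155 days. The SAP result is 'Missing'.

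**5. Effect on the table.** If T events truly last 15 days or more and a share f of them is ongoing or lacks a complete stop date, the top row shows T × (1 − f). The documents give no value for f, so the following range is assumed, with T = 20.

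| f | Shown in top row |
|---|---|
| 10% | 20 × 0.90 = 18 |
| 25% | 20 × 0.75 = 15 |
| 50% | 20 × 0.50 = 10 |

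Only the part of this shortfall with a documented minimum of at least 15 days can be recovered.

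**The case against.** The strongest reply is that 'Missing' is often the accurate label. Stop dates are actively sought only for related AEs. An unrelated AE with a blank stop date becomes ongoing through the default in protocol 9.2.2.3.3, footnote a, without anyone having seen it persist. The footnote gives a status and says nothing about length.

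The 6-month call is also no routine check on ordinary non-serious AEs. Protocol 5.1.4 has it ask about SAEs, including hospitalized suspected dengue, and protocol 11.1 describes a questionnaire on SAEs and AEs of particular interest. After the last injection, the last routine check on an ordinary AE is V08. The exceptions are related AEs and those that led to discontinuation, which are followed until they resolve, stabilise or become chronic.

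This part of the reply stands. A reader might infer that every ongoing or blank-dated AE is a long event, and that about 155 days is a typical minimum. The documents do not support that. Counting every blank stop date up to the last contact would put unobserved events into the top row and replace possible undercounting with possible overcounting.

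It is also fair to say that no event is lost. The 'Missing' row is displayed, outcome is summarised separately (SAP 4.4.1.4.3), and days within the solicited period are still tabulated (Table 4.5). The safety analyses are descriptive and the rule is explicit. None of this, however, restores the duration category in cases where the record already determines it.

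**Conclusion.** The concern holds in a limited form. The SAP sends all ongoing and partly dated events to 'Missing', including those whose recorded data establish the top category. The row for "15 days or more" (unsolicited AEs and SAEs) and the ≥ 8 and ≥ 15 day rows (solicited reactions) can therefore undercount persistent events.

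The number affected is unknown. It depends on how many events have a documented minimum that reaches the cut-off, and neither document allows an estimate. The 18, 15 and 10 out of 20 above illustrate assumed shares only. The effect stays within descriptive safety tables and does not touch the non-inferiority tests, power or sample size. It is a cheap improvement worth making, with modest consequences if left undone.

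**What to change.** Keep the SAP 5.3.1.5 principle that stop dates are not imputed. Amend SAP 4.4.1.2.4 and 4.4.1.1.6 (with Table 4.6), and add a cross-reference in 5.3.1.5, so that the duration category is assigned from the documented minimum when that settles it:

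- **Partial stop date:** use the earliest date consistent with the known month and year, minus the start date, plus 1.
- **Event recorded as ongoing:** use the last date on which it was documented as present, minus the start date, plus 1. That date may be V08, or the 6-month contact for SAEs and for related AEs followed to resolution.
- **Solicited reaction ongoing under 4.4.1.1.7:** use the days counted in the solicited period plus at least 1.
- **Other events recorded as ongoing:** show them in a separate 'Ongoing' row.
- **'Missing':** keep it for blank stop dates with no documented persistence, including unrelated AEs that are ongoing only by the footnote default, and for partial dates that do not settle the category.

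Do not substitute the last-contact or termination date for all blank stop dates.

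The cost is SAP wording, slightly more programming and one more table row. No new data are needed.
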